- There will be approximately 4 Children's Health sites utilized for the study; COACH Clinic, Children's Medical Center Dallas, Children's Health Plano, and Children's Specialty Center in Dallas. All participants will be recruited at one of these 3 sites. There will be 3 follow-ups with participants in the pilot study. They will be followed over the course of 18 months. This begins 12 months before surgery. During this time the participant will have a preoperative survey and will be given the intervention. After this period they will have two post-operative surveys at 3 months and 6 months respectively. For the focus group and key informant participants they will be required to participate in only one focus group or interview lasting no more than an hour to an hour and a half. If focus group participants are unable to attend focus group due to scheduling conflicts, time constraints or transportation issues they will have the option of participating in an in-depth phone interview, online-video interview or completing a survey. These interviews or survey will also take up to an hour to an hour and a half to complete.
- The PI will also gather medical records of each participants such as pre-surgery BMI and post-surgery BMI and obesity related co-morbidity information to determine the effectiveness of the intervention program in supporting the health outcomes post-surgery. SDOH data will also be pulled from the medical records and will be compared to a similar patient population.

EMR data will be gathered up to 18 months post-surgery.

Study Measures

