3. Threat of Danger to Others
4. Hospitalization (psychiatric, drug related)
5. Death

- *Procedures to safeguard against adverse events:* All data collection protocols include a form on which research staff members record any problems with the data collection, concerns about the study subject or unusual occurrences during the collection. These forms allow our research staff an opportunity to quickly review and respond to any possible concerns or adverse effects. All adverse events will be monitored and supervised by the Principal Investigator.
- *Informed Consent:* All participants will be required to read and sign detailed consent/assent forms before participating in the study. Participants are advised of the voluntary nature of this program and of their right to withdraw from the study at any time and/or request that information about themselves and their family be removed from data analyses. Each participant receives a verbal and written description of the study. Experienced research staff members are available at all points of the study process to answer questions and to explain assessment procedures, uses to which the data will be put, and confidentiality of data. Because our population consists of Hispanic participants, all project documents, including the consent/assent forms, will be available in both Spanish and English, and will be administered according to the expressed preference of the participant. If a staff member

determines that a participant's reading skills are limited, all materials will be presented verbally in Spanish or in English, as indicated. Assessment questionnaires and anthropometric, cardiometabolic and biological measurements will be explained and conducted in the participant's preferred language (Spanish or English).

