Participants' hospitalization (both for physical and psychiatric conditions) will be documented and reported (see reporting procedures for serious adverse events below).

5. Death

If a project staff member is advised of the death of a participant, the project staff member will document the death in the participant's study file and report the death to the PI.

Reporting procedures for adverse events

An Adverse Events and Serious Adverse Events form will be used to record any events.

The anticipated potential adversity inherent in assessment is limited to those situations described above and is addressed by the timely intervention of a licensed project facilitator skilled in risk assessment and mandatory reporting requirements.

The prevalence of adverse events described above will be reported both to our IRB and to NIH through annual progress reports. We will also report adverse events to others, as directed by our IRB or NIH Program Official.

Reporting Procedure for Serious Unanticipated Adverse Events

In the event of an unanticipated serious adverse event, the project PI will ensure that these events are reported to the NIH Program Official and the University of Texas IRB within 24 hours by phone, fax, and/or email and will submit a written report to the Program Official within two days. The project staff will utilize the following reporting procedures:

1. When the project staff and/or PI become aware of a serious adverse event, reporting requirements must be implemented in a timely manner.
2. PI completes a Serious Adverse Event Reporting Form and submit the form to the University of Texas IRB within two days. Serious adverse events include any hospitalizations or other life-threatening conditions (see serious adverse events above). All serious adverse events will be examined for the need for appropriate referral, an assessment of relatedness to the project, the need for any additional documentation and/or follow-up, and modification of the Informed Consent and notification of existing participants. All adverse events that are ongoing will be followed until they stabilize or resolve. [name] will resolve each adverse events or serious adverse event and will consult with the IRB, as necessary.
3. The PI will review the study protocol and determine what further action to take based on the best interests of the participants and of the research and submit to the IRB for approval.

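### No active way of finding hospitalizations and deaths is stated, so events in participants who stop attending, or after the 6-month visit, may go unrecorded although medical records are already extracted

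*Combined protocol and SAP*

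**What the plan says.** The list of serious adverse events under Data and Safety Monitoring includes hospitalization and death, and the later Serious Adverse Events section repeats both. On how they come to be recorded, the text gives three statements:

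- Death: "If a project staff member is advised of the death of a participant", that person notes it in the study file and reports it to the PI.
- Hospitalization: "Participants' hospitalization (both for physical and psychiatric conditions) will be documented and reported". No source, scheduled question or record search is named.
- Serious events in general (Reporting Procedure for Serious Unanticipated Adverse Events): "When the project staff and/or PI become aware of a serious adverse event, reporting requirements must be implemented in a timely manner".

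Study Procedures describes the record extraction: "The PI will also gather medical records of each participants such as pre-surgery BMI and post-surgery BMI and obesity related co-morbidity information". Its stated purpose is to judge effectiveness. Social-determinants data are drawn from the same records for a comparison with similar patients, and EMR collection runs to 18 months after surgery. Nothing links this extraction to serious events.

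Direct follow-up after surgery lasts 6 months, with assessments at 3 and 6 months (Study Design).

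**The concern.** Awareness is a normal trigger for starting a reporting clock. The difficulty is that, for admissions and deaths, nothing earlier in the process is designed to produce the awareness. A participant who is admitted, or who stops attending because of an event, may be among those least likely to tell staff.

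The yearly review under Oversight, the monthly Data Safety Board review (last item under Quality control and assurance) and the reports to the IRB and NIH all depend on what has been reported. In a group of about 20, one missed admission can be the difference between a report of one event and a report of none.

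**Working it through.** **Step 1: what reaches whom.** The provisions that could bring an admission or death to light are:

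- Suicidality: the coordinator must review flagged questionnaire items. This is active, but needs a completed questionnaire.
- Abuse and threats to others: looked for during assessments. This needs attendance.
- Concerns form in every data collection protocol: needs a data collection.
- Research assistant calls about missed surveys or content (Intervention Delivery): these do reach non-attenders, but no safety question is specified.
- Sessions after surgery: at least 20 in 6 months, or about one every 9 days (182/20 ≈ 9). These give frequent contact with participants who attend.
- Medical record extraction: covers each participant to 18 months after surgery. It does not depend on attendance at sessions, but no safety field is named.

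Two gaps remain: participants who stop attending, and the 18 − 6 = 12 months between the last study visit and the end of EMR collection. The documents do not say whether serious-event reporting is meant to continue through those 12 months.

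**Step 2: how many drop-outs the plan expects.** Statistical Power for AIM 3 gives 20 subjects, about 10% attrition and 22 recruits. 20 × 1.10 = 22 reproduces the stated figure; 20/(1 − 0.10) = 22.2 would round up to 23. Expected drop-outs are 22 × 0.10 = 2.2, so about 2.

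**Step 3: size under assumptions.** The documents give no admission risk and no capture rate, so both are varied. Let p be a participant's chance of at least one reportable admission. Take 20 participants, independent and with equal risk.

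- All captured: P(none recorded) = (1 − p)^20
- All events in 2 drop-outs lost: (1 − p)^18
- Capture fraction c in everyone: (1 − cp)^20

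| Assumed p | All captured | 2 drop-outs lost | 80% capture | 50% capture |
|---|---|---|---|---|
| 5% | 0.95^20 = 36% | 0.95^18 = 40% | 0.96^20 = 44% | 0.975^20 = 60% |
| 10% | 0.90^20 = 12% | 0.90^18 = 15% | 0.92^20 = 19% | 0.95^20 = 36% |
| 15% | 0.85^20 = 4% | 0.85^18 = 5% | 0.88^20 = 8% | 0.925^20 = 21% |

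At p = 10% the expected number of participants with a recorded admission is 20 × 0.10 = 2.0, 18 × 0.10 = 1.8, 20 × 0.08 = 1.6 and 20 × 0.05 = 1.0 respectively.

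**Step 4: chance that the drop-out gap matters at all.** The chance that at least one of 2 drop-outs is admitted is 1 − (1 − p)^2: 10% at p = 5%, 19% at 10%, 36% at 20% and 51% at 30%. If drop-outs carry a 30% risk and the other 18 carry 10%, the true chance of no admission is 0.90^18 × 0.70^2 = 0.150 × 0.49 = 7%, against 15% for none recorded.

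**The case against.** Three stronger readings are tempting, and the documents do not support them.

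- A reader might infer that serious events of every kind are recorded only when staff happen to hear of them. That is wrong for suicidality, abuse and threats, which have stated checks at assessments. The point covers hospitalization and death only.
- A reader might infer that events in drop-outs will be missed. Only about 2 drop-outs are expected, and the research assistant pursues missed surveys and content. Sessions are run from a co-investigator's clinic, and the 3- and 6-month clinical measures are standard of care. Any of these may bring an event to light, so the supportable word is may.
- A reader might take the move from 12% to 36% as the size of the problem. It rests on 50% capture in all 20 participants, a figure with no source. Losing every event in 2 drop-outs gives 15%.

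It can also be said that the record items are introduced by "such as pre-surgery BMI and post-surgery BMI and obesity related co-morbidity information", which is open-ended, and that the hospitalization sentence is unconditional. Both are true. But a list that permits further items does not require a safety search, and a commitment to report admissions does not say how they will be found.

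Finally, this is a single-group pilot of a behavioural programme whose procedures the protocol calls minimal risk, and no serious-event rate is an efficacy endpoint. An undercount would bias no effect estimate. It would weaken the safety record, which is reason enough for an inexpensive change.

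**Conclusion.** The concern holds for hospitalization and death, in participants who stop attending and in the 12 months after the last study visit. The plan makes these events reportable, states no active way of finding them, and gives no safety use to an extraction that could help. Whether any event would be lost is unknown.

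At an assumed 10% admission risk, the chance of recording none moves from 12% to between 15% and 36%, depending on whether only 2 drop-outs are lost or half of all events are. These figures rest on equal, independent risks and on assumed admission and capture rates. They cover neither deaths nor months 6 to 18 separately. The change should be made because it costs little and the safety reviews depend on the count, not because a large undercount has been shown.

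**What to change.** 1. Add hospital admissions, other than the planned surgical admission, and deaths to the EMR extraction. Apply this to every enrolled participant, including those who stopped sessions, over the full window to 18 months after surgery.
2. State what consent allows after withdrawal. Informed Consent lets participants withdraw and ask for their information to be removed from analyses, and the plan does not say whether extraction then continues.
3. Set the dates of the record pulls, which the plan does not schedule, and say whether serious-event reporting covers months 6 to 18.
4. Ask about outside-hospital admissions in the 3- and 6-month surveys.
5. Enter each hit on the serious adverse event form.
6. Reconcile the scope of hospitalization so that extractors know what counts. The list under Data and Safety Monitoring reads "Hospitalization (psychiatric, drug related", whereas the later section covers physical as well as psychiatric conditions.

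The search supplements awareness-based reporting. Periodic pulls cannot by themselves meet the 24-hour and two-day limits, and the Data Safety Board's 24 hours run from occurrence. The cost is a few extraction fields and one survey item. Events outside the health system may still be missed, particularly after 6 months, when no survey is planned.

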- **Statistical Power for AIM 3.** A single-factor, repeated measures design with a sample of 20 subjects, measured at baseline, 3-, and 6-months, achieves 80% power to detect a contrast using a multivariate T² test at a 0.01 significance level. We reduce the type I to a more conservative 1% to correct for multiplicity. The standard deviation across subjects at the same time point is assumed to be 1. The pattern of the covariance matrix is to have all correlations equal with a correlation of 0.25 between the first and second time point measurements.¹⁰⁰⁻¹⁰³ The value of the contrast applied to the hypothesized means is 1.⁹⁷ However, since we are anticipating an attrition rate of ~10%, we will recruit 22 adolescent MBS patients.

Data and Safety Monitoring

- *Data and Safety Monitoring:* All subjects will have an assigned unique study identification number used on all data forms and instruments. Data are computer-linked to the remainder of the dataset on

each individual, and linking information between personal identifiers and study numbers is kept in a locked file cabinet in the Principal Investigator's Office. Certain program staff (e.g., principal investigator, clinical team of [name], [name], and [name], study coordinator) will have access to confidential information needed to perform their respective duties, but the rest of the research staff are not privy to confidential information.

- *Potential Adverse Events.* None of the proposed procedures involve invasive methods of data collection. Most of the proposed methods are part of, or an extension of, the standard of care to assess pre-post MBS surgery mental and physical health and are minimal risk. These studies present minimal discomforts to the patient. Should any adverse events occur during this protocol, the medical facilities at University of Texas are prepared to care for the study participants. All participants will be debriefed regarding any serious health information that might be discerned in the protocol.
- *Description of Adverse and Serious Adverse Events:* Adverse events and serious adverse events identified for study participants that will be reported during protocol are: Adverse Events
 1. Family Crises
 2. Possible Violation of Confidentiality
 3. Extreme Distress due to Assessment Procedures
 4. Extreme Embarrassment or Distress in
Response to Disclosing Sensitive Personal Information

Serious Adverse Events

1. Suicidal Thoughts or Attempts
2. Abuse

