- This study was designed around the maximum sample size possible given the logistical limitations of the study (time, expense). For a total sample size of 25 subjects (Aim 3, the power associated with any of the independent effects in any of the proposed statistical models will be approximately 80% (P value cutoff = .01) as long as the effect accounts for 3% of the total variance relative to the model specific error term (i.e., $R^2 = .03$). This will be true for any effect that is included in any of the statistical models either pre or postoperative and includes both main effects and possible interactions. The power will change slightly due to the complexity of the model and the number of independent effects included, but overall, considering the tradeoff between increased efficiency and loss of error degrees of freedom in more complex models, the power will remain at approximately 80% when 3% of the variance is explained. This axiom also holds no matter the scale of measurement (i.e., continuous or discrete). An R^2 of .03 equates to a "d" statistic (i.e. Cohen's d) of approximately .35. According to Cohen's taxonomy for the social sciences, this is a small to medium effect size. Effects accounting for less than 3% of the total variance are most likely of limited clinical significance. As previously stated in the statistical methods, considering the observational nature of the investigation, we have chosen to use a more conservative P value cutoff. More importantly this conservative standard also increases the chances of reproducibility and helps to account for the amount of statistical modeling/testing that increases the likelihood of irreproducible results.

Ethics

- For all study participants the initial consent process will take place during recruitment process by clinical staff and research staff. However, if a willing participant does not have time to learn about, and sign all consent forms, study staff will schedule a follow up time with them to consent. If needed participants will be allowed to take consent home to review before speaking to research staff or clinical staff administer consent.

Data handling and record keeping

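### The Statistics section claims about 80% power at P < .01 with 25 subjects for any effect with R² = .03; its own inputs give about 4% between subjects and, on labelled assumptions, 11% to 17% within subjects.

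*Combined protocol and SAP*

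**What the plan says.** The plan has two power statements for Aim 3.

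- **Statistics section.** It begins "For a total sample size of 25 subjects" and says that "the power associated with any of the independent effects in any of the proposed statistical models will be approximately 80" percent at a P value cutoff of .01, provided the effect explains 3% of the variance relative to the model's error term. It equates R² = .03 with a Cohen's d of about .35. It applies the claim to every effect in every model, before or after surgery, on any measurement scale; the claim "includes both main effects and possible interactions". It adds: "Effects accounting for less than 3% of the total variance are most likely of limited clinical significance". The same section says that the sample size was the largest that logistics allowed.
- **Statistical Power for AIM 3 (under Study Measures).** "A single-factor, repeated measures design with a sample of 20 subjects" is said to give 80% power at the 0.01 level for a contrast tested with a multivariate T² test. The SD is 1, the covariance has "all correlations equal with a correlation of 0.25 between the first and second time point measurements", and "The value of the contrast applied to the hypothesized means is 1". To allow for about 10% attrition, "we will recruit 22 adolescent MBS patients".

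Study Design and the Aim 3 text under Study Measures also give 20 subjects.

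**The concern.** With 25 subjects and a 1% significance level, only large effects can be detected reliably. An effect explaining 3% of the variance is small to medium by the plan's own description, so 80% power for it is implausible on sight. It is more so for interactions and for any model.

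The two statements also sit badly together. The second gives about 80% power at the same alpha for a contrast of 1 with an SD of 1. Five more subjects cannot bring the detectable effect down from that order to .35.

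What is at stake is interpretation. The section dismisses effects below 3% of variance as clinically unimportant and claims 80% power at that threshold. Read together, these suggest that a non-significant result rules out any effect worth knowing about. The plan has no rule for interpreting null results, so this is a risk and not a stated intention.

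**Working it through.** **Inputs.** From Statistics: n = 25, alpha = .01, R² = .03, d about .35, claimed power about 80%. From Statistical Power for AIM 3: three time points, SD 1, correlation r = .25, contrast of 1, n = 20. Sidedness is not stated; I take t tests as two-sided.

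**Step 1: the effect-size conversion.** f² = .03/.97 = .0309 and d = 2·√.0309 = .352. The plan's conversion is right. The power is not.

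**Step 2: between-subject effect, 1 df.** Noncentral F with 1 and n − 2 df and λ = n·f². At n = 25, λ = 25 × .0309 = .773.

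| n | Power, R² = .03, alpha .01 |
|---|---|
| 25 | 4.0% |
| 22 | 3.5% |
| 20 | 3.2% |

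A 2-df effect at n = 25 has 2.7%. The smallest n giving 80% for the 1-df effect is 381.

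**Step 3: within-subject change.** The Statistics section gives no correlation, so each reading needs an assumption, named below. The paired rows use the noncentral t with n − 1 df and noncentrality dz·√n. The three-time-point rows use λ = 3n·f²/(1 − r); at n = 25 this is 75 × .0309/.75 = 3.09.

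| Reading at n = 25 | Power |
|---|---|
| Paired, d on the outcome SD, r = .25: dz = .35/√(2 × .75) = .286 | 11% |
| Three-time-point T², r = .25, as F(2, 23) | 11% |
| Three-time-point repeated-measures F(2, 48), r = .25 | 13% |
| Paired, d on the change-score SD: dz = .35 (equivalent to r = .5) | 17% |

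The n for 80% is 147 with dz = .286 and 99 with dz = .35.

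**Step 4: what would produce 80%?**

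- One-sided testing at .01 raises the paired readings only to 16% and 25%.
- Treating all 75 observations as independent gives 14%.
- Relaxing alpha to .05 gives 13% between subjects.
- The correlation would have to be about .89 for the paired test, or about .85 for the repeated-measures F (80.5% at .85). The plan assumes .25. Even then, between-subject effects would stay at 4%.

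**Step 5: comparison with the other power statement.** The contrast coefficients are not given. Read as a difference between two time points, the contrast of 1 is dz = 1/√1.5 = .816, with 77% power at n = 20. Read as baseline against the mean of the two follow-ups, dz = .943 and power is 90%. A figure near 80% therefore goes with a standardized change of roughly .8 to .9, not .35.

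**Step 6: what is detectable with 80% power at alpha .01.**

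| n | Single within-subject contrast (SD of change score) | Between-subject R², 1 df | Omnibus 2-df T² (multivariate standardized distance) |
|---|---|---|---|
| 20 | .84 | .42 | .95 |
| 22 | .79 | .39 | .90 |
| 25 | .73 | .35 | .83 |

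**The case against.** The strongest points on the other side are these.

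- **The within-subject range rests on borrowed inputs.** The 11% takes its correlation from a separate power statement, and the 17% implies r = .5, which the plan never states. At an assumed correlation of .75, power would be 39% to 52%. If R² is read as a partial R² on the within-subject error, power falls to about 4% to 6%. This stands as a caution: the 4% is the direct recomputation, and the within-subject figures depend on their stated assumptions. None reaches 80%.
- **The planned test is a T² test, so paired-t detectable effects may be optimistic.** This stands in part. The plan speaks of one contrast, which is a 1-df test, and the values .84/.79/.73 fit that. An omnibus 2-df T² would need about .95/.90/.83, so the revised text must name the test.
- **The consequence is limited.** Aim 3 is a proof-of-concept study, logistics set the sample size, and the other power statement roughly reproduces. This is true, and it limits the harm. It does not make the 80% figure correct.
- **The mismatch of 25 with 20 and 22 subjects is a separate point.** Agreed. It hardly affects the power error (4.0% against 3.2%), but it decides which detectable effect should be quoted.

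**Conclusion.** The concern holds. The gap is 80% claimed against 4.0% for a 1-df between-subject effect, which needs no input beyond those in the Statistics section. Within subjects it is 80% against 11% (r = .25, d on the outcome SD) to 17% (d on the change-score SD), with two-sided tests assumed. An R² = .03 between-subject effect would be missed about 96% of the time. At n = 25, 80% power requires R² of about .35, more than ten times the stated value. The conclusion is insensitive to sidedness, to the choice among 20, 22 and 25 subjects, and to whether the effect is between or within subjects. The comparison with the other power statement shows tension rather than an exact contradiction, because the contrast there is not fully specified.

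**What to change.** 1. Delete the R² = .03 power claim from the Statistics section, with its extension to all main effects, interactions and measurement scales.
2. Reconcile the Aim 3 sample size: 25 in Statistics; 20 analysed and 22 recruited in Statistical Power for AIM 3; 20 in Study Design and in the Aim 3 text under Study Measures.
3. For the reconciled number of evaluable subjects, state the effect detectable with 80% power at alpha .01, and name the test. At n = 20, 22 or 25, give .84, .79 or .73 SD of the change score for a single 1-df within-subject contrast, and R² of .42, .39 or .35 for a 1-df between-subject effect. If the omnibus T² over three time points is meant, give its own values from the table above.
4. Add that smaller effects, including R² = .03, are not powered.

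The cost is protocol wording only. The stated detectable effect becomes less favourable. No patients are added, and no test or endpoint changes.

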Model that allows for variation in type and scale characteristics of the independent effects, the GZLM extends this versatility to include various types of dependent variables.⁹⁹ In GZLM, the relationship between the independent variables and the dependent outcomes is specified by way of a link function that defines the functional form of this relationship (e.g., when the dependent variable is a proportion, a logistic link function might be used). Through different specifications of the link and probability functions, one generalized model is used to examine the statistical relationships between the design parameters (i.e., independent variables) and the dependent variables, regardless of their scale properties. Statistical consideration is given to repeated measures (pre-, 3-, 6-month post-MBS data). Since the time component has only 2 levels (e.g., 1 pre, 2 post-MBS), there are minimal statistical complications associated with the autocorrelation structure of repeated measures. Measures taken at baseline will be included in the GZLM as covariates to ensure pretest balance and as a control on regression to the mean. Changes in weight will be analyzed by employing a generalization of the t-test, known as Hetelling's T² test. This approach is very important in this case, since it same approach employed in the design. We shall assume a more conservative type I error of 1% to adjust for multiplicity.¹⁰⁰ Missing Values: GZLM models will efficiently use the longitudinal data and accommodate attrition that is ignorable (essentially, missing at random, MAR).¹⁰¹ To assess sensitivity to MAR we will use approaches for the multivariate normal setting and others if normality is not reasonable.¹⁰¹ This avoids the problem of eliminating subjects with incomplete repeated measurements. SAS and JMP (SAS Institute, Cary, NC) will be the primary statistical software packages. *Quality Control.* PI [name] will coordinate the QA/QC protocol with clinical and research staff. Appropriate checks will be conducted prior to, during, and after the completion of data collection.

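### With one group, a centred baseline covariate in the GZLM change model shrinks the standard error of the mean change without making the estimate more precise

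*Combined protocol and SAP*

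**What the plan says.** Study Measures, Data Analysis Plan, makes the Aim 3 dependent measure the change from before to after surgery and assigns the Table 2 outcomes (weight loss, BMI, excess weight loss, body composition, cardiometabolic profile) to a generalized linear model (GZLM). It then says "Measures taken at baseline will be included in the GZLM as covariates", giving two reasons: balance at pretest and protection against regression to the mean. It does not say whether the covariate is centred, which coefficient is tested, or how the standard error is formed. The same paragraph sends weight change to Hotelling's T², with no covariates mentioned, and adds "We shall assume a more conservative type I error of 1% to adjust for multiplicity".

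Statistical Power for AIM 3 gives a one-group design with 20 subjects at three time points, SD 1, "all correlations equal with a correlation of 0.25 between the first and second time point measurements", a contrast of 1, and a T² test at the 0.01 level.

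The Statistics section claims about 80% power at a P cutoff of .01 for 25 subjects, "as long as the effect accounts for 3% of the total variance relative to the model specific error term", and applies this to "any effect that is included in any of the statistical models either pre or postoperative and includes both main effects and possible interactions". On larger models it states that, "considering the tradeoff between increased efficiency and loss of error degrees of freedom in more complex models, the power will remain at approximately 80" per cent. That section does not name covariates; the Data Analysis Plan does.

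**The concern.** Baseline adjustment sharpens a comparison between two groups because it removes chance baseline differences between them. Aim 3 has no second group, so there is nothing to balance. Its question is the mean change in these patients.

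When change is modelled on baseline centred at the sample mean, the model treats that sample mean as known. Its standard error answers the question of change at this sample's mean baseline, not mean change in such patients. If the sample's baseline happens to be high, the expected fall back is counted as change and its uncertainty disappears from the error bar. The covariate therefore does not control regression to the mean in this estimate.

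At stake are the GZLM intervals for mean change and the 1% level, which is the plan's only stated protection against multiplicity.

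**Working it through.** **The plan's own figures.** With n = 20, SD 1, all correlations 0.25, and a step of 1 at both post-surgery visits, the two-df T² test has noncentrality 17.8 on 2 and 18 df and power 78.9%, in line with the stated 80%. A single baseline-to-follow-up contrast has SD √(2 × 0.75) = 1.225, standard error 1.225/√20 = 0.274, noncentrality 3.65 and power 77.4%. These inputs are used below.

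The Statistics section's 80% does not reproduce. For N = 25 and R² = 0.03 the noncentrality is 25 × 0.03/0.97 = 0.77, and two-sided power at 0.01 is 4.0%. That is a separate and larger fault; nothing below depends on it.

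**Model examined.** D = post minus pre, regressed on pre minus its sample mean; complete data; identity link; intercept tested with its model standard error.

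1. The intercept equals the raw mean of D exactly, so its true variance is σ_D²/n, with or without the covariate.
2. The printed standard error is s_res/√n, where σ_res² = σ_D²(1 − R²).
3. One post visit: σ_D² = 2(1 − ρ) = 1.5 and cov(D, pre) = ρ − 1 = −0.75, so R² = 0.5625/1.5 = 0.375.
4. Average of 3 and 6 months: the average has variance (1 + ρ)/2 = 0.625, so σ_D² = 0.625 + 1 − 0.5 = 1.125 and R² = 0.5625/1.125 = 0.50.
5. Ratio of printed to true standard error: √0.625 = 0.79 and √0.50 = 0.71. Allowing for s_res on 18 df, the averages are 0.78 and 0.70.
6. Under normality the mean of D is independent of s_res, so true size = 2P(t₁₈ > 2.878 × √(1 − R²)). The thresholds become 2.276 and 2.035, giving 3.5% and 5.7%. Simulation with 100,000 trials per setting gave 3.5% and 5.7%, against 1.0% unadjusted.

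True size of a nominal 1% test, n = 20:

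| Correlation | R², one visit | Size, one visit | R², average | Size, average |
|---|---|---|---|---|
| 0.25 (plan) | 0.375 | 3.5% | 0.50 | 5.7% |
| 0.5 | 0.25 | 2.3% | 0.33 | 3.0% |
| 0.8 | 0.10 | 1.4% | 0.13 | 1.5% |
| 0.9 | 0.05 | 1.2% | 0.07 | 1.2% |

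At correlation 0.25 the sizes are 3.5% and 5.5% with n = 18, and 3.7% and 5.9% with n = 25.

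**Apparent power.** For a true change of 1 SD at one visit, the adjusted test rejects about 91% of the time; the valid paired test has 77%. The difference comes from the short standard error.

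**Where no inflation appears.** Size stays near 1% for the unadjusted test, for 6 versus 3 months, for a covariate unrelated to change, and when the mean is evaluated at a known baseline value. With all three visits as responses and baseline as a main effect only, exchangeable GEE fits gave the same time contrast and standard error, to four decimals, with and without the covariate.

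**A robust standard error is not a cure.** For the average of two visits, an HC3 standard error still rejected about 4% in 3,000 simulated trials, against 5% for ordinary least squares in the same trials.

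**The case against.** A reader might infer that the plan's stated 1% test runs at 3.5% to 5.7%. The documents do not support that. The test powered at 0.01, and named for weight change, is Hotelling's T² without covariates, and it keeps its level.

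A reader might also infer that the Statistics section relies on covariates for its efficiency gain. It does not mention them, and its claim covers slopes and interactions, where extra terms can properly reduce residual error.

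The strongest objection is that the plan does not specify the faulty model. It lists the pre-surgery visit among the repeated measures, and if that visit is a response row with baseline as a main effect only, the problem does not arise. This stands as a limit on the claim. It does not remove it: the dependent measure is defined as change, baseline measures are to be covariates, and modelling change on baseline is the most direct reading. Centring at the sample mean is the natural choice, since change at a baseline weight or glucose of zero has no meaning.

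Two further points stand. The size of the effect depends on a planning correlation of 0.25 and is small at 0.8 or above. And the statement that a covariate cannot sharpen the estimate is exact only with complete data; with the expected attrition of about 10%, baseline values can recover some information.

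**Conclusion.** The point holds for GZLM tests and intervals of one-group mean change when change is modelled with a sample-mean-centred own-baseline covariate and a model-based standard error. At the plan's n = 20 and correlation 0.25, a nominal 1% test then has a true level of about 3.5% (one post visit) or 5.7% (average of two). At correlation 0.5 it is about 2.3% or 3.0%, and at 0.8 about 1.4% to 1.5%. The point estimate is unaffected.

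The result assumes complete, normally distributed data, equal SDs and correlations, own baseline as the only covariate, and an identity link; proportion outcomes with a logistic link were not calculated. It does not extend to the T² test of weight change, to a model with all three visits as responses and baseline as a main effect only, or to between-patient effects. Because the Data Analysis Plan permits the affected model on its most direct reading, the text should be corrected before analysis.

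**What to change.** In the Data Analysis Plan, estimate and test one-group mean change from a repeated-measures model with pre-surgery, 3 and 6 months as response rows, time as the only factor, and no own-baseline covariate. With complete data and an unstructured covariance, the standard error of each change is then the SD of change over √n. Under MAR the model still uses baseline data from participants who miss follow-up. For outcomes that are already changes (raw weight loss, excess weight loss), use the post-surgery rows only, again without the own-baseline covariate.

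If an adjusted model is kept, take its standard error from a bootstrap that resamples participants and recomputes the covariate mean each time. Keep baseline covariates for questions about which patients change more, and drop pretest balance as a reason for them.

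In the Statistics section, state that the efficiency argument does not apply to the one-group mean change.

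The cost is wording, plus wider GZLM intervals for mean change: roughly 25% (one visit) to 40% (average of two) at correlation 0.25, and less at higher correlations. The T² analysis does not change.
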